**5. METHODS*****Main study parameter***

To determine whether or not a sentinel node procedure in patients with ovarian cancer is feasible by injecting the tracers into the ovarian ligaments instead of into the ovary itself.

The lymphatic drainage of the ovary follows the lymph vessels that accompany the ovarian artery and vein in the infundibulopelvic ligament up to the high para-aortic region and renal vein. The exact mechanism of drainage to pelvic area is still unclear. It may follow the lymph vessels adjacent to the uterus towards the pelvic lymph nodes.

Through a sentinel node procedure the first node(s) that receives primary lymphatic flow should be identified (the so-called sentinel node(s)). In case of lymphatic spread, this lymph node will be the first lymph node obtaining a metastasis.

In this feasibility study we will include both patients with (suspicion of) ovarian cancer as well as patients with a high-risk uterine carcinoma. The latter group of patients can also be included because these patients obtain the same surgical procedure; a total abdominal hysterectomy (TAH) with bilateral salpingo-oophorectomy (BSO) and a pelvic and para-aortic lymphadenectomy of lymph node sampling.

### ***Secondary study parameters***

In order to test the reliability of the sentinel node detection by injection in the ovarian ligaments, some secondary study parameters are also important:

- The anatomical location(s) and number of the sentinel node(s), visualized at surgery by either blue dye or the radioactive tracer
- The incidence of false negative lymph nodes, i.e. in contrast to the sentinel lymph node, one of the resected non-sentinel lymph nodes contains tumor cells. To calculate the percentage of false negative lymph nodes: the number of patients with negative sentinel lymph node(s) AND positive non-sentinel lymph node(s) is the numerator, the true amount of negative lymph nodes is the denominator."

The golden standard would be to perform a complete pelvic and para-aortic lymphadenectomy. However, the Dutch guideline advises a comprehensive lymph node sampling as standard treatment. We feel such a golden standard can be considered in subsequent study, when this study provides evidence that a sentinel node procedure in this way indeed is feasible. Nevertheless, a possible false negative result obtained in this study is important and therefore will be documented.

- The incidence of unrecognized sentinel nodes

Recognition of sentinel nodes with blue dye and the gamma probe during surgery is less reliable than by making a scintigram. Therefore ideally, as in breast and vulvar cancer, a scintigram is made before surgery to recognize the sentinel nodes so that during surgery no sentinel nodes will be missed. However, this principle cannot be accomplished in patients with ovarian cancer, because the tracers cannot be injected at the appropriate sides without opening the abdomen. However, we expect that missing sentinel nodes in patients with ovarian cancer occurs less frequent because the area where the sentinel nodes can reside is restricted to well described areas. Nevertheless, by making a scintigram 24 hours after surgery, at least an impression is obtained on the incidence of unrecognized sentinel lymph nodes.

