### Objective:

- 1) To determine whether or not a sentinel node procedure in patients with ovarian cancer is feasible when the tracers are injected in the ovarian ligaments.
- 2) To determine the anatomical localisations of the sentinel nodes.
- 3) To determine the incidence of false negative sentinel nodes.

**Study design:** phase I feasibility study.

**Study population:** the following patients will be included:

- Patients with a high suspicion of an ovarian malignancy in whom a median laparotomy and a frozen section analysis is planned.
- Patients with endometrial cancer in whom a staging laparotomy is planned.

**Intervention (if applicable):** After opening the abdomen, before starting the surgical staging procedure, blue dye and the radioactive-colloid will be injected in the ligamentum ovarium proprium and the ligamentum infundibulo-pelvicum. This will be done on the ovary with suspicion of malignancy (patients with an ovarian tumour) or one of the normal ovaries (patients with endometrial cancer).

**Main study parameters:** percentage of patients in whom it is feasible to identify sentinel nodes. Other study parameters are the anatomical localisation of the sentinel node(s) and the incidence of false negative lymph nodes.

**Nature and extent of the burden and risks associated with participation, benefit and group relatedness:** the surgery is prolonged with 20-25 minutes due to the required

incubation time after injection of the blue dye and radioactive isotope. A scintigram will be performed 24 hours after the surgery to determine whether residual radioactive lymph nodes

can be detected. The scintigram will only be performed if the patient is capable to be transported to the nuclear department. No extra blood samples will be taken, no extra visits, physical examinations or other tests are necessary. There is no risk of tumour dissemination by injecting the tracers in the ovarian ligaments. There is a 0,07 to 2,7% risk of an allergic reaction to the blue dye. The dose of radioactive isotope given does not give adverse side effects, either to the patients or the personnel present in the operating theatre.

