***Sample size calculation***

Between 24 and 28 patients will be included in the study.

The sample size calculation is based on the fact that:

- with a group of 20 evaluable patients the study group is large enough to give an answer whether sentinel node(s) can be detected related to the ovarian lymphatic flow when the tracers are injected in the ovarian ligaments. For this purpose both patients with an ovarian and endometrial malignancy, planned for a staging laparotomy can and will be included.
- patients with a benign result on frozen section of the suspicious ovary will be excluded from the study because no lymph node(s) will be resected in these patients. These patients will be documented and described in the report after the study.
- based on retrospective data, in 60% of the patients with a suspicious ovary, frozen section will confirm a ovarian malignancy.
- to calculate one of the secondary endpoints (incidence of false negative sentinel lymph node) at least 10 patients with ovarian cancer should be part of the 20 evaluable patients.

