## **7. STATISTICAL ANALYSIS**

***Descriptive statistics***

Registered items:

- Sentinel nodes
  - o Number per patient
  - o Location(s) per patient
  - o Number(s) of sentinel nodes containing a metastasis per patient
  - o Location of sentinel nodes containing a metastasis per patient
- Non-sentinel lymph nodes removed during the subsequent staging procedure
  - o Number per patient
  - o Location(s) per patient
  - o Number(s) containing a metastasis per patient
  - o Location of non sentinel nodes containing a metastasis per patient

Based on the above registered items the median and mean number of sentinel nodes and its main locations can be determined. By combining the data of the sentinel en non-sentinel nodes, cases in which de sentinel node is false negative can be identified

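### As worded, the false-negative measure admits endometrial cancer patients, in whom a uterine nodal metastasis would be scored against the ovarian sentinel node

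*Protocol*

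**What the plan says.** Protocol Section 5, Secondary study parameters, introduces the false-negative measure as a test of the reliability of sentinel node detection and gives an explicit formula: "the number of patients with negative sentinel lymph node(s) AND positive non-sentinel lymph node(s) is the numerator", and "the true amount of negative lymph nodes is the denominator". No tumour type is named. The Summary objectives and Section 2 list the same measure, also without a restriction. Section 7, Descriptive statistics, says only this: "By combining the data of the sentinel en non-sentinel nodes, cases in which de sentinel node is false negative can be identified".

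The Summary puts the tracer at the suspicious ovary in ovarian patients, and at "one of the normal ovaries (patients with endometrial cancer") otherwise. Section 5, Surgical procedures, alternates the side from one endometrial patient to the next. These patients then have sentinel nodes removed, followed by sampling of other nodes, and the histology is recorded (Data collection).

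Section 4, Sample size calculation, separates two purposes. For the question of whether sentinel nodes can be detected, it says: "For this purpose both patients with an ovarian and endometrial malignancy, planned for a staging laparotomy can and will be included". For the false-negative endpoint it says that "at least 10 patients with ovarian cancer should be part of the 20 evaluable patients".

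**The concern.** A sentinel node predicts nodal status when the tracer follows the drainage of the tumour. Section 5, Main study parameter, relies on this when it says that the sentinel node is the first to be involved if there is lymphatic spread. In endometrial patients the tracer follows the drainage of an ovary that does not hold the primary tumour, on a side chosen by alternation. A positive non-sentinel node beside a negative sentinel node in such a patient may simply reflect spread from the uterus along another route.

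The formula as written would still count that patient as a false negative. The reason given for including endometrial patients is that they undergo the same operation. That supports using them for detection and drainage mapping, but not for nodal prediction.

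At stake is the only measure in the study that speaks to whether a negative ovarian sentinel node can be trusted. It will rest on very few node-positive patients. If its population is left open, the choice could also be made after the results are known.

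**Working it through.** **Inputs from the Protocol.** 20 evaluable patients, at least 10 with ovarian cancer (Sections 3 and 4). Frozen section confirms malignancy in 60% of suspicious ovaries, and 24 to 28 patients are to be included (Section 4). Nodal metastasis occurs in 14.2% of clinical stage I-II ovarian carcinoma (Section 1, Background).

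**Assumed inputs.** The Protocol does not give endometrial node positivity (p, taken as 5-30%) or the share of those node-positive patients whose ovarian sentinel node is negative (m, taken as 25-100%).

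**Step 1: the plan's own figure.** 10 / 0.60 = 16.7, so 17 patients with a suspicious ovary. Adding 10 endometrial patients gives 27, inside the stated 24 to 28. A split of 10 ovarian and 10 endometrial evaluable patients is therefore one that the plan accommodates, and 10 is the largest endometrial number that the minimum allows.

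**Step 2: node-positive ovarian patients.** Expected number: 10 x 0.142 = 1.42. Chance of at least one: 1 - (1 - 0.142)^10 = 0.784. Chance of none: 0.216.

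**Step 3: endometrial patients meeting the numerator.** Expected number: 10 x p x m. Chance of at least one: 1 - (1 - p x m)^10.

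| p | m | Expected | Chance of at least one |
|---|---|---|---|
| 5% | 25% | 0.125 | 1 - 0.9875^10 = 0.12 |
| 10% | 50% | 0.50 | 1 - 0.95^10 = 0.40 |
| 14.2% | 50% | 0.71 | 1 - 0.929^10 = 0.52 |
| 20% | 80% | 1.60 | 1 - 0.84^10 = 0.83 |
| 30% | 100% | 3.00 | 1 - 0.70^10 = 0.97 |

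**Step 4: effect on the result.** Suppose that the ovarian sentinel node misses nothing in ovarian patients. The share of node-positive patients scored as missed, as a ratio of expected counts, should then be 0%. Pooled over both tumour types it becomes:

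- p = 5%, m = 25%: 0.125 / (1.42 + 0.50) = 6.5%
- p = 14.2%, m = 50%: 0.71 / (1.42 + 1.42) = 25%
- p = 30%, m = 100%: 3.00 / (1.42 + 3.00) = 68%

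This share is shown only for scale. It is not the Protocol's percentage, whose denominator is worded in negative lymph nodes.

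**Step 5: sensitivity to the number of endometrial patients.** At 28 inclusions and 20 evaluable, 8 frozen sections are benign, so 8 / 0.40 = 20 patients had a suspicious ovary. That leaves 12 ovarian and 8 endometrial evaluable patients. The range in Step 3 becomes 1 - 0.9875^8 = 0.10 to 1 - 0.70^8 = 0.94.

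**The case against.** The strongest reply is that Section 4 already points to an ovarian basis. It pools the two tumour types for detection, and gives the false-negative endpoint as the reason for requiring 10 ovarian cancers. A reader might infer from Section 5 that the Protocol definitely counts endometrial patients. The documents do not support that: no passage says that they are counted, and none says that they are excluded. This part of the reply stands. However, a minimum of 10 within 20 is equally compatible with a calculation over all 20, and neither the formula nor Section 7 carries a restriction.

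A second reply is that the analysis set of a descriptive secondary measure can be left to a statistical analysis plan, which may exist but is not at hand. That would answer a missing detail. Here the Protocol gives its own formula, and following it literally yields the wrong count.

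A third reply is that little depends on the figure. Early termination uses only the detection rate and accrual. Section 5 defers the reference standard of complete lymphadenectomy to a later study and promises only to document false negatives. This stands and limits the severity.

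Other stronger readings also fail:

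- **Spurious events equal or exceed true false negatives.** This cannot be derived. The 1.42 counts node-positive ovarian patients, and no ovarian false-negative rate is given.
- **Node-negative endometrial patients count as true negatives.** The denominator is worded as nodes, not patients. That mismatch of units is a separate matter.
- **Endometrial findings say nothing about ovarian drainage.** This is too strong. Sections 1 and 5 describe a possible ovarian route beside the uterus to the pelvic nodes, so the routes may overlap.
- **Bilateral ovarian tumours raise the same problem.** The Protocol describes one suspicious ovary and does not address bilateral disease.

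**Conclusion.** The point holds as a defect of wording with a real consequence. The formula in Section 5 and the text in Section 7 admit endometrial patients, and do not carry over the ovarian basis that Section 4 suggests. A uterine metastasis could then be reported as a failure of the ovarian sentinel node.

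With about 1.4 node-positive ovarian patients expected, one such event could dominate the figure. The chance of at least one among 10 endometrial patients is about 12-97%. The width of that range reflects two assumed rates that the Protocol does not give. The calculation also assumes the maximum of 10 endometrial patients, a sentinel node found in each of them, and independence between patients. The 1.4 assumes that the 14.2% for clinical stage I-II disease applies to the ovarian patients enrolled and to the node sampling used.

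Severity is moderate: the measure is secondary and descriptive, and no stopping rule depends on it.

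**What to change.** In Section 5, Secondary study parameters, add that the numerator and the denominator of the false-negative measure are both computed in patients with ovarian cancer only. Repeat this in Section 7, Descriptive statistics, where false-negative cases are identified. Report sentinel and non-sentinel histology of endometrial patients in a separate descriptive listing, without labelling them false or true negatives. Keep these patients for the detection rate and for mapping of drainage.

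The cost is a sentence or two in each section. Tumour type is already recorded under Data collection, so no procedure, data item or sample size changes. The downside is a smaller denominator for this secondary endpoint. With 10 ovarian patients there is a 21.6% chance that none is node-positive, in which case no false negative could occur. Pooling would not cure this, because the added patients do not test prediction of spread from an ovarian tumour.

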### ***Background***

EOC can metastasize through three different ways [3,4]: intraperitoneal (in the abdominal cavity), lymphogenous and haematogenous. Concerning the lymphogenous spread, it is clear that lymphatic metastases of EOC mainly occur in the para-aortic lymph nodes [5]. It is believed that the tumour cells follow the lymph vessels that accompany the ovarian artery and vein in the infundibulopelvic ligament up to the high para-aortic region and renal vein. Nevertheless, pelvic lymph node metastases are also frequently found [6-16]. These tumour cells probably follow a different route, following the para-uterine vessels in the broad ligament towards the uterine artery and vein and further on to the iliac vessels. In some case reports isolated inguinal node metastases are also described [17-20]. The exact mechanism of this route of metastasis is still unclear, but the metastatic cells might follow the course of the round ligament towards the inguinal lymph nodes, or might follow the iliac vessels towards the femoral vessels. The incidence of lymph node metastasis in clinical stage I-II ovarian carcinoma is 14.2% [21].

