### ***Staging***

In case of a clinical early stage ovarian cancer, the Dutch guideline [1] recommends a staging laparotomy with adequate lymph node sampling, with an absolute minimum of ten lymph nodes removed. In the same guideline, a footnote is made stating that a larger number of removed lymph nodes will increase the chance of finding metastases. These lymph nodes also need to be sampled from different anatomical regions, of which the most important are the

para-aortic and paracaval region between the renal vein and inferior mesenteric artery, the common, internal and external iliac vessels and the obturator fossa.

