#### *During surgery*

Removal of lymph nodes:

- systematic lymphadenectomy / lymph node sampling

Approaches range from taking some lymph nodes only (lymph node sampling) to systematic lymphadenectomy [22]. A systematic lymphadenectomy can be seen as the golden standard. However, such a radical procedure gives more late morbidity than lymph node sampling. These include the formation of lymphocyst (up to 13.5%), nerve and vessel injury (up to 4%) and increased blood loss and operating time [26, 27].

- removal of sentinel node(s)

Through a sentinel node procedure the first node that receives primary lymphatic flow can be identified (the so called sentinel node). The pathological examination is an indication of the nodal status of the remaining nodes. If the sentinel node is negative, the patient may be spared a radical lymphadenectomy and thus the morbidity that can be caused by it [28].

The sentinel node technique has been proven effective in other cancers such as breast cancer and malignant melanoma. In the gynaecological field it has been shown to be effective in vulvar cancer. Currently sentinel node studies are done for cervix en uterine cancer. Studies done for sentinel node in ovarian cancer are very limited. One article that describes the role of sentinel lymph node sampling in gynaecological cancers, only briefly mentions ovarian cancer. The authors state that the procedure is difficult due to the often bulky mass ovarian tumours. Furthermore, with injecting in the ovary there is a possible risk of tumour dissemination [28].

*Nyberg et al.* have done a study in 16 patients with high-risk uterine cancer in which technetium and blue dye were injected in the right or left ovary [29]. They used an incubation time of 15 minutes. In this study patients were included with a high-risk uterine carcinoma because these patients obtain the same operation as patients with clinical early stage ovarian cancer: a total abdominal hysterectomy (TAH) with bilateral salpingo-oophorectomy (BSO) and a pelvic and para-aortic lymphadenectomy or lymph node sampling. In 15 out of 16 patients the sentinel node was detected. Another study used activated charcoal solution to identify ovarian lymphatics in 11 patients. The charcoal was injected in the cortex of the ovary. The charcoal was deposited in the lymph nodes of all patients [12].

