### **3. STUDY DESIGN**

Observational feasibility study to detect sentinel nodes: mapping the lymphatic drainage of the ovaries.

The study will end after 20 patients, of which at least 10 patients with ovarian cancer, are included in which the complete sentinel node procedure has been performed. The expected inclusion period is estimated to be two years. If the detection rate of the sentinel node is less than 50%, or when less 5 patients are included in a year, the study will end prematurely.

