### **Surgical procedures**

#### *Patients with a high suspicion of a malignant ovarian tumour*

After making the median incision and opening the abdomen, before starting with removal of the enlarged and suspicious adnex, blue dye and the radioactive isotope will be injected in the ligamentum ovarii proprium (median side) and the ligamentum infundibulo-pelvicum (lateral side), close to the ovary and just below the peritoneum. Four syringes will be made containing 0.2 ml patent blue and 0.15 ml (20-MBq) radioactive isotope (99mTc-nanocolloid or Nanocoll®, GE Healthcare, Eindhoven, The Netherlands, see appendix for information leaflet) will be given. Mixing patent blue and radioactive isotope does not affects the quality of the two substances, nor does it give extra or different side effects for the patient [36]. The

99mTc-nanocolloid is prepared by trained laboratory staff on the nuclear lab in a sterile 'class A' Laminar Air Flow (LAF) hood. Afterwards patent blue is added and the syringe is mixed. This is done 30 minutes before the start of the surgery.

A 15-minute interval will be planned after injection. The exact time interval for detection of positive nodes is unclear. Common practice is to wait for 15 minutes, if in this time period the node is not detected, it is considered negative. In daily practice a wait of more than 15 minutes during surgery is not workable. At 5 and 10 minutes the radioactivity will be measured along the lymphatic tract to document whether or not perhaps sentinel node(s) can be identified at a shorter time-interval in future studies. A Geiger counter measures the radioactivity. The Geiger counter will be the same device in all surgeries.

After the 15 minutes time-interval the adnex will be removed and admitted to the pathologist for a frozen section. If the result is benign, no further actions will be performed in these patients. If the result is malignant, the sentinel node(s) will be identified either (once more) by the radioactive tracer and / or visually (blue dye) after opening the retroperitoneal space.

After removal of the sentinel node(s) a complete standard staging procedure will be performed including a comprehensive at random sampling of other lymph nodes at the different locations.

Surgical steps related to the study (standard or extra):

- Median laparotomy (standard care)
- Injection of blue dye and radioactive isotope (extra for the study)
- 15 minute waiting time during the surgery (extra for the study)

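### The false-negative percentage divides patients by negative lymph nodes, and no reading of that denominator gives the share of node-positive patients missed

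*Protocol*

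**What the plan says.** The third objective in the protocol summary is "To determine the incidence of false negative sentinel nodes", and section 2 lists the same item as a secondary objective. Section 5, Secondary study parameters, presents it as one of the checks on how reliable the detection is, and prescribes a formula. The numerator is the number of patients whose sentinel nodes are negative and who have a positive non-sentinel node. The rule ends: "positive non-sentinel lymph node(s) is the numerator, the true amount of negative lymph nodes is the denominator".

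No other section supplies a denominator. The sample size section links the endpoint to a minimum case mix: "at least 10 patients with ovarian cancer should be part of the 20 evaluable patients". Section 7 says only that false-negative cases can be found by combining the sentinel and non-sentinel data.

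Two other places bear on the meaning. The introduction gives the clinical purpose: "If the sentinel node is negative, the patient may be spared a radical lymphadenectomy". The surgical procedure for suspected ovarian tumours says of the 15-minute wait that "if in this time period the node is not detected, it is considered negative".

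**The concern.** A percentage needs one unit, and its base decides what it measures. Here patients are divided by something worded as nodes. Someone who sees a false-negative percentage in a sentinel node study will probably take it as the share of patients with nodal disease whom the sentinel node failed to reveal. The prescribed ratio cannot be that under any reading, because node-positive patients are never its base. When nodal disease is uncommon, as the protocol expects in early-stage ovarian cancer, the printed figure is much smaller than the share missed and can look reassuring when it should not.

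This is not a detail left for an analysis plan. The protocol fixes a formula, and a later plan would have to reinterpret or contradict it.

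**Working it through.** The protocol states no numerical false-negative rate, so there is no figure to reproduce. The check is to apply each reading of the formula to the same data.

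**Notation (patients).** TP: at least one positive sentinel node. FN: all sentinel nodes negative, a non-sentinel node positive. TN: all nodes negative. The share of node-positive patients missed is FN/(FN+TP).

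**Inputs from the protocol.**
- Ten ovarian cancers, the minimum in the sample size section.
- Node-positive rate p = 0.142, from Background: "The incidence of lymph node metastasis in clinical stage I-II ovarian carcinoma is 14.2" per cent.
- Ten nodes per patient, used only for the node-count reading, from the guideline minimum under Staging: "with an absolute minimum of ten lymph nodes removed".

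**Example (assumed): ten patients, a sentinel node found in all, TP = 1, FN = 1, TN = 8.**
- Denominator read as truly node-negative patients: FN/TN = 1/8 = 12.5%. The numerator is not part of this denominator, so it is not a proportion.
- Denominator read as sentinel-negative patients: FN/(FN+TN) = 1/9 = 11.1%. This is one minus the negative predictive value.
- Denominator read as nodes: 1/80 = 1.25% if only the nodes of the eight TN patients count; 1/98 = 1.0% if all 100 nodes count, less one positive node in each of the two node-positive patients.
- Share of node-positive patients missed: 1/2 = 50% (exact 95% CI 1.3% to 98.7%).

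**What the patient readings print if a share f of metastases is missed and a sentinel node is found in everyone.** FN/TN = f·p/(1−p), and FN/(FN+TN) = f·p/(f·p + 1−p). At p = 0.142:
- f = 1 (every metastasis missed): 0.142/0.858 = 16.6%, and 0.142/1 = 14.2%.
- f = 0.5: 0.071/0.858 = 8.3%, and 0.071/0.929 = 7.6%.

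FN/TN is therefore smaller than the share missed by a factor of (1−p)/p = 0.858/0.142 = 6.0.

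**Sensitivity to p.** The inclusion criteria set no stage limit, so 14.2% is an assumption for this population. The protocol's own subgroup figures for early disease run from 2.6% (mucinous) to 23.3% (serous). Missing every metastasis prints 2.6% to 2.7% at the lower end (0.026/0.974 = 2.7%) and 23.3% to 30.4% at the upper end (0.233/0.767 = 30.4%).

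**Node-positive patients available.** At p = 0.142 and n = 10, the expected number is 10 × 0.142 = 1.42, and the chance of none is 0.858^10 = 21.6%.

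**The case against.** **The patient readings nearly agree.** The numerator says patients and section 7 speaks of cases, so few analysts would divide by nodes. The two patient readings differ little: 12.5% against 11.1%, or 8.3% against 7.6%. This stands. A reader might infer that two analysts would publish widely different percentages; that is unlikely unless one of them takes the node wording literally. The large gap is between every reading and the share missed.

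**The base is a choice.** The documents promise an incidence of false negatives, not a sensitivity. FN/(FN+TN) is a sound measure and answers the introduction's question about sparing lymphadenectomy. This also stands, but the protocol neither names that measure nor words its denominator that way. It also does not show how much nodal disease the technique finds.

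**Non-detection.** A reader might infer from the surgical procedure that a patient with no detected sentinel node is counted as sentinel-negative, which would mix detection failures with wrong results. The text does not support that as the natural reading. The sentence concerns waiting time before any histology exists, the search is repeated after the retroperitoneal space is opened, and data collection records nodal pathology as a separate item. Sections 3, 5 (premature termination) and 7 (interim analysis) treat non-detection as a matter of detection rate. Negative there most likely means not found by tracer; a clarifying line is enough.

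**Population.** A reader might infer that the calculation is confined to ovarian cancer patients. The sample size section asks that enough of them be included; it does not exclude the others.

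**Consequence.** No decision uses the percentage: early stopping depends on accrual and on detection ("If the detection rate of the sentinel node is less than 50" per cent). Per-patient histology is registered, so any ratio can be rebuilt. The protocol also concedes that sampling is not the gold standard. All of this limits the severity, but does not make the formula right.

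**Conclusion.** The definition is wrong as written. It mixes units, its denominator is undefined, and under no reading does it give the share of node-positive patients missed. In the ten-patient example it prints 12.5%, 11.1% or about 1% where that share is 50%. At a 14.2% node-positive rate with full detection, a technique that found no metastasis at all would print 14.2% to 16.6% on the patient readings. These sizes rest on the assumed counts, on 14.2% applying to this population and, for the node reading only, on ten nodes per patient.

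Severity is minor to moderate: a listed objective carries a faulty formula, but it is secondary and descriptive, and neither the primary detection rate nor any stopping rule is affected.

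**What to change.** In section 5, Secondary study parameters, count patients in both parts:
- **Denominator:** patients with at least one detected and histologically examined sentinel node and any positive node, sentinel or not.
- **Numerator:** those among them whose examined sentinel nodes are all negative.
- **Presentation:** x/y. An exact interval, and a rule for y = 0, can be set here or in an analysis plan.
- **Risk after a negative sentinel node, if wanted:** report FN/(FN+TN) separately and call it one minus the negative predictive value.
- **Population:** say whether the ratio covers ovarian cancer patients only or all evaluable patients. This is the authors' choice.
- **Clarification only:** state that, for this calculation, the surgical-procedure wording on undetected nodes means not detected by tracer. Such patients are reported as detection failures, with their number beside the ratio, and are not counted as having negative sentinel nodes.

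The cost is a wording change; the data collection and statistical sections already register sentinel and non-sentinel histology. The downside is imprecision. With ten ovarian cancers at 14.2%, about 1.4 node-positive patients are expected, with a 22% chance of none. Leaving out patients without a detected node lowers this further. At the 15/16 detection of the cited ovarian injection study, 10 × 0.142 × 15/16 = 1.3 are expected (24% chance of none); at the 50% stopping limit, 10 × 0.142 × 0.5 = 0.7 (48%). Using all 20 evaluable patients with full detection would give 20 × 0.142 = 2.8 (0.858^20 = 4.7% chance of none), if 14.2% also held for the endometrial patients, for whom the protocol gives no rate.
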